8.3. Adverse Events, Serious Adverse Events, and Product Complaints

The definitions of the following events can be found in Appendix 10.3:

- Adverse events (AEs)
- Serious adverse events (SAEs)
- Product complaints (PCs)

These events will be reported by the participant (or, when appropriate, by a caregiver, surrogate, or the participant's legally authorized representative).

The investigator and any qualified designees are responsible for detecting, documenting, and recording events that meet these definitions and remain responsible for following up events that are serious, considered related to the study intervention or study procedures, or that caused the participant to discontinue the study (see Section 7).

After the initial report, the investigator is required to proactively follow each participant at subsequent visits/contacts. All SAEs and AEs of special interest (as defined in Section 8.3.3) will be followed until resolution, stabilization, the event is otherwise explained, or the participant is lost to follow-up (as defined in Section 7.3). For PCs, the investigator is responsible for ensuring that follow-up includes any supplemental investigations as indicated to elucidate the nature and/or causality. Further information on follow-up procedures is provided in Appendix 10.3.

8.3.1. Timing and Mechanism for Collecting Events

All SAEs will be collected from the signing of the ICF until the follow-up visit at the time points specified in the SoA (Section 1.3).

All AEs will be collected from the signing of the ICF until participation in the study has ended.

Adverse events that begin before the start of study intervention but after signing of the ICF will be recorded on the Adverse Event eCRF.

Although all AEs after signing the ICF and Assent Form (as applicable) are recorded by the site in the eCRF/electronic data entry, SAE reporting to the Sponsor begins after the participant has signed the ICF and has received study intervention. However, if an SAE occurs after signing the ICF, but prior to receiving ixekizumab, it needs to be reported ONLY if it is considered reasonably possibly related to study procedures.

All SAEs will be recorded and reported to the Sponsor or designee immediately and under no circumstance should this exceed 24 hours, as indicated in Appendix 10.3. The investigator will submit any updated SAE data to the Sponsor within 24 hours of it being available. Participants with a serious hepatic AE should have additional data collected using the electronic data entry.

Investigators are not obligated to actively seek AEs or SAEs after conclusion of the study participation. However, if the investigator learns of any SAE, including a death, at any time after a participant has been discharged from the study, and he/she considers the event to be reasonably related to the study intervention or study participation, the investigator must promptly notify the Sponsor.

8.3.2. Pregnancy

Collection of pregnancy information

Male participants with partners who become pregnant

- The investigator will attempt to collect pregnancy information on any male participant's female partner who becomes pregnant while the male participant is in this study. This applies only to male participants who receive intervention.
- After learning of a pregnancy in the female partner of a study participant, the investigator will:
 - obtain a consent to release information from the pregnant female partner directly; and
 - within 24 hours after obtaining this consent, will record pregnancy information on the appropriate form and submit it to the Sponsor.

The female partner will also be followed to determine the outcome of the pregnancy. Information on the status of the mother and child will be forwarded to the Sponsor. Generally, the follow-up will be no longer than 6 to 8 weeks following the estimated delivery date. Any termination of the pregnancy will be reported regardless of gestational age, fetal status (presence or absence of anomalies), or indication for the procedure.

Female participants who become pregnant

The investigator will collect pregnancy information on any female participant who becomes pregnant while participating in this study. The initial information will be recorded on the appropriate form and submitted to the Sponsor within 24 hours of learning of a participant's pregnancy.

- The participant will be followed to determine the outcome of the pregnancy. The investigator will collect follow-up information on the participant and the neonate and the information will be forwarded to the Sponsor. Generally, follow-up will not be required for longer than 6 to 8 weeks beyond the estimated delivery date. Any termination of pregnancy will be reported, regardless of gestational age, fetal status (presence or absence of anomalies) or indication for the procedure.
- While pregnancy itself is not considered to be an AE or SAE, any pregnancy complication or elective termination of a pregnancy for medical reasons will be reported as an AE or SAE.
- A spontaneous abortion (occurring at <20 weeks gestational age) or still birth (occurring at ≥20 weeks gestational age) is always considered to be an SAE and will be reported as such.
- Any post-study pregnancy-related SAE considered reasonably related to the study intervention by the investigator will be reported to the Sponsor as described in protocol Section 8.3.1. While the investigator is not obligated to actively seek this information in former study participants, he/she may learn of an SAE through spontaneous reporting.
- Any female participant who becomes pregnant while participating in the study will discontinue study intervention. If the participant is discontinued from the study, follow the standard discontinuation process and continue directly to the follow-up phase. The follow-up on the pregnancy outcome should continue independent of intervention or study discontinuation.

8.3.3. Adverse Events of Special Interest

The following adverse events of special interest (AESIs) will be used to determine the safety and tolerability of ixekizumab over the range of doses selected for this clinical study.

Adverse events of special interests for ixekizumab are the following:

- cytopenias (leukopenia, neutropenia, and thrombocytopenia),
- liver function test changes/enzyme elevations (ALT, AST, bilirubin, and ALP),
- infections,
- injection-site reactions,
- allergic reactions/hypersensitivities,
- cerebro-cardiovascular events,
- malignancies,
- inflammatory bowel disease (IBD), and
- depression.

Sites will provide details on AEs as instructed on the eCRF. Investigators will also educate participants and/or caregivers about the symptoms of systemic allergic/hypersensitivity reactions and will provide instructions on the management and reporting of these reactions. Blood samples will be collected as soon as possible for any participant who experiences an AE of a potential systemic allergic/hypersensitivity reaction during the study, as judged by the investigator. These samples may be tested for antidrug antibodies (ADAs), other laboratory tests needed to elucidate the cause of the allergic/hypersensitivity reaction, and/or ixekizumab serum concentration.

8.4. Pharmacokinetics

Pharmacokinetics parameters are not evaluated in this study.

8.5. Pharmacodynamics

Pharmacodynamic parameters are not evaluated in this study.

8.6. Genetics

Genetics are not evaluated in this study.

8.7. Biomarkers

Biomarkers are not evaluated in this study.

8.8. Health Economics or Medical Resource Utilization and Health Economics]

Health economics or medical resource utilization and health economics parameters are not evaluated in this study

9. Statistical Considerations

The SAP will include a more technical and detailed description of the statistical analyses described in this section. This section is a summary of the planned statistical analyses of the most important endpoints, including primary and key secondary endpoints.

9.1. Statistical Hypotheses

No statistical hypotheses testing is planned for this study.

9.2. Analyses Populations

The following analysis populations will be used; additional analysis populations will be specified in the SAP:

Analysis Population	Description
PsO with No Active PsA – Modified Intent-to-Treat (mITT) Population	Unless otherwise specified, efficacy and health outcomes analyses specific to psoriasis will be conducted on the PsO with No Active PsA - mITT population, defined as all enrolled participants with a psoriasis indication, who do not qualify for Active PsA and receive at least 1 dose of study treatment, even if the participant does not receive the correct treatment, or otherwise does not follow the protocol.
Active PsA – mITT Population	Unless otherwise specified, efficacy and health outcomes analyses specific to PsA will be conducted on the Active PsA mITT population, defined as all enrolled participants with an Active PsA indication who receive at least 1 dose of study treatment, even if the participant does not receive the correct treatment, or otherwise does not follow the protocol.
Safety Population	Safety analyses will be conducted on the safety population, defined as all enrolled participants who receive at least 1 dose of study treatment. Participants will be analyzed according to the treatment to which they are assigned.

9.3 Missing Data Imputation

The following methods for imputation of missing data will be used:

9.3.1 General Nonresponder Imputation for Clinical Response

Analysis of categorical efficacy and health outcomes variables will be assessed using a nonresponder imputation (NRI) method. Participants will be considered a nonresponder for the NRI analysis if they:

- do not meet the clinical response criteria (e.g., ACR20, PASI75, PASI90, PASI100, sPGA [0,1]);
- have missing clinical response data at a timepoint of interest (e.g., Week 12, Week 24);
- discontinue study treatment at any time prior to a timepoint of interest for any reason; or
- have no postbaseline observation.

The NRI may be applied at any time point specified for analysis.

9.4 Study Participant Disposition and Characteristics

9.4.1 Study Participant Disposition

All participants who prematurely discontinue from the study treatment and/or from the study will be identified, and the extent of their participation in the study will be reported.

Patient disposition will be summarized for each treatment period with reasons for discontinuation.

9.4.2 Study Participant Characteristics

Participant demographic characteristics and baseline clinical measures will be summarized overall. Baseline characteristics will include sex, age, age category, weight, body mass index, race, and other demographic characteristics as per the SoA (Section 1.3).

9.4.3 Concomitant Therapy

Previous and concomitant medications will be summarized for participants who enter treatment and will be presented by the World Health Organization (WHO) Anatomic Therapeutic Class (ATC) Level 4 and WHO preferred term (PT).

9.4.4 Treatment Compliance

Treatment compliance with investigational product will be summarized for participants who enter the treatment. A participant will be considered overall compliant for treatment if he/she is missing no more than 20% of the expected doses, does not miss 2 consecutive doses, and does not over-dose (i.e., take more injections at the same time point than specified in the protocol).

Proportions of participants compliant by visit and overall will be reported.

9.5 Statistical Analyses

9.5.1. General Considerations

Statistical analysis of this study will be the responsibility of Lilly.

Unless otherwise specified, continuous data will be summarized in terms of the mean, standard deviation, minimum, maximum, median, and number of observations. Categorical data will be summarized as frequency counts and percentages.

Baseline will be defined as the last non missing assessment recorded on or prior to the date of first injection for efficacy and health outcomes. In most cases, this will be the measure recorded at Week 0 (Visit 2). Change from baseline will be calculated as the visit value of interest minus the baseline value. For safety analyses using a baseline period, the baseline period is defined as the time from Visit 1 to the date/time of the first injection.

Any change to the data analysis methods described in the protocol will require an amendment ONLY if it changes a principal feature of the protocol. Any other change to the data analysis methods described in the protocol, and the justification for making the change, will be described in the clinical study report (CSR). Additional exploratory analyses of the data will be conducted, as deemed appropriate.

Complete details of the planned analyses will be documented in the SAP.

9.5.2 Primary Endpoint Analysis

The primary analysis, the number and percentage of participants in the safety population experiencing:

- TEAEs,
- TEAE by maximum severity,
- Death,
- SAEs,
- TEAE related to study treatment,
- AEs leading to treatment discontinuation, and
- TEAEs of special interest (hepatic, cytopenias, infections, allergic reactions/hypersensitivities, injection-site reactions, cerebrocardiovascular events, major adverse cerebrocardiovascular events [MACE], malignancies, depression, IBD, interstitial lung disease [ILD]).

These AEs, occurring within the duration of the study (24 weeks) after being started on Ixekizumab, will be summarized. For events that are gender-specific (as defined by the Medical Dictionary for Regulatory Activities [MedDRA]), the denominator and computation of percentage will include only participants from the given gender.

Refer to Section 9.5.5.1 for further details.

9.5.3 Secondary Endpoint(s) Analysis

Endpoints Specific to Psoriasis (PsO) and Psoriatic Arthritis (PsA) Participants with 3% or More BSA of PsO

As a part of the secondary analyses, the following endpoints will be summarized (i) for the PsO indication and will be based on the PsO with no active PsA – mITT population, and (ii) for the active PsA indication and will be based on the active PsA – mITT population with BSA of PsO $\geq 3\%$ at baseline, unless otherwise specified:

Proportion of Participants with sPGA (0 or 1)

The proportion of participants achieving sPGA response of 0 or 1 at Week 12 will be summarized and the associated 95% confidence interval (CI) will be provided using normal approximation. Missing data will be imputed using the NRI method as defined in Section 9.3.1. Further details will be provided in SAP.

Proportion of Participants with PASI 75

The proportion of participants achieving a PASI 75 response at Week 12 will be summarized and the associated 95% CI will be provided using normal approximation. Missing data will be imputed using the NRI method as defined in Section 9.3.1. Further details will be provided in SAP.

Endpoints Specific to Psoriatic Arthritis (PsA)

As a part of the secondary analyses, the following endpoint will be summarized for the PsA indication and will be based on the active PsA-mITT population:

Percentage of Participants Achieving ACR20

The proportion of participants achieving a response of ACR20 at Week 24 (Visit 15) will be summarized and 95% CI will be provided using normal approximation. Further details will be provided in SAP.

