2.3. Benefit/Risk Assessment

Ixekizumab has been demonstrated to be safe and effective for the treatment of participants with moderate-to-severe chronic PsO and/or active PsA. The risk profile for participants within this study is anticipated to be consistent with the known safety experience for ixekizumab.

More information about the known and expected benefits, risks, SAEs, and reasonably anticipated AEs of ixekizumab are found in the IB. Information on AEs expected to be related to the study intervention may be found in Section 6.2 (DCSI) of the IB. Information on SAEs that are expected in the study population independent of drug exposure and that will be assessed by the Sponsor in aggregate periodically during the course of the study, may be found in Section 5 (Effects in Humans) of the IB.

Taking into account the measures taken to minimize risk to participants participating in this study, the potential risks identified in association with ixekizumab are justified by the anticipated benefits that may be afforded to participants with PsO or PsA.

3. Objectives and Endpoints

Objectives	Endpoints
Primary	

 To assess the type of adverse event (AE) and the proportion of Indian participants with plaque psoriasis (PsO) and participants with psoriatic arthritis (PsA) reporting AEs and serious adverse events (SAEs) occurring within the duration of the study (24 weeks) after being started on ixekizumab. 	
 AEs including SAEs, treatment-emergent adverse events (TEAEs), and adverse events of special interest (AESIs) during the treatment periods (Week 0 to Week 24)
Secondary	
Specific to Psoriasis Group	

 To evaluate percentage of participants Achieving a $\geq 75\%$ Improvement in Psoriasis Area and Severity Index (PASI) 	
 Proportion of participants who achieve the following PASI scores: PASI 75 (defined as 75% improvement from baseline in PASI) at Week 12

 To evaluate percentage of participants with a Static Physician Global Assessment (sPGA) (0,1) 	
 Proportion of participants with an sPGA score of 0 or 1 (0, 1) at Week 12
Specific to Psoriatic Arthritis Group	

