4.1. Overall Design

Study RHCZ is a prospective, multicenter, open-label, single-arm, Phase 4 study with 4 study periods assessing outcomes in terms of AEs and SAEs with ixekizumab when used in participants aged ≥ 18 years for PsO and PsA in Indian population (Section 1.2).

The following treatment will be assessed in this study for PsO participants with no active PsA and PsA participants who meet criteria for moderate-to-severe PsO:

- Ixekizumab: 80-mg subcutaneous (SC) injection.
 - At Week 0, 160-mg starting dose (two 80-mg injections), followed by 80 mg Q2W from Weeks 2 through 12, and then followed by 80 mg Q4W thereafter (i.e., at Weeks 16 and 20).

The following treatment will be assessed in this study for PsA participants who do not meet criteria of moderate-to-severe PsO:

- Ixekizumab: 80-mg SC injection.
 - At Week 0, 160-mg starting dose (two 80-mg injections), followed by 80 mg Q4W (i.e., at Weeks 4, 8, 12, 16 and 20).

The study will consist of 4 periods:

- **Period 1 (Section 4.1.1): Screening Period** (Visit 1) will assess participant eligibility and occurs approximately 5 to 28 days prior to Period 2 (baseline; Week 0 [Visit 2]).
- **Period 2 (Section 4.1.2): Induction Dosing Period** occurring from Week 0 (baseline; Visit 2) to Week 12 (Visit 5).
- **Period 3 (Section 4.1.3): Maintenance Period** occurring after Week 12 (Visit 5) to Week 24 (Visit 6).
- **Period 4 (Section 4.1.4): Post-Treatment Follow-Up Period (PTFU)** occurring from last treatment period Week 24 (Visit 6) or early termination visit (ETV), for a minimum of 4 weeks following that visit.

All procedures to be conducted during the study, including timing and sequence (as necessary), are indicated in the Schedule of Activities (SoA; Section 1.3). Appendix 10.2 lists the specific laboratory tests that will be performed for this study.

Participants discontinuing from the study intervention who have received at least 1 dose of study intervention will continue to the ETV prior to entering to the PTFU period (Period 4) (see Section 7). For the management of participant safety, all participants should be monitored through Period 4 at least as frequently as indicated on the SoA (Section 1.3).

Treatment group is described in Section 6.1, Table RHCZ.6.1, and administration of the study intervention is described in Section 6.1, Table RHCZ.6.2.

Excluded and restricted therapies are detailed in Section 6.8.

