- Women who are infertile due to surgical sterilization (hysterectomy, bilateral oophorectomy, or tubal ligation) and congenital anomaly such as Müllerian agenesis.

[3] Have given written informed consent approved by Lilly, or its designee, and the Investigational Review Board (IRB)/ERB governing the site.

[4] Willing to self-administer study intervention.

For PsO Participants

[5] Present with chronic PsO based on a confirmed diagnosis of chronic PsO vulgaris for at least 6 months prior to baseline (Week 0; Visit 2).

[6] Have $\geq 10\%$ BSA of psoriasis at screening (Visit 1) and baseline (Week 0; Visit 2).

[7] Have both an sPGA score of ≥ 3 and PASI score ≥ 12 at screening (Visit 1) and baseline (Week 0; Visit 2).

- [8] Are a candidate for phototherapy and/or systemic therapy.

For PsA Participants

- [9] Have a diagnosis of active PsA for at least 6 months (based on a detailed medical history provided by the patient, and a physical exam by the Study Investigator, and/or other evidence such as that provided by joint x-rays, that establishes a history consistent with a diagnosis of active PsA of at least 6 months' duration) and currently meet the Classification for PsA (CASPAP) criteria (Section 10.6).
- [10] Have active PsA defined as the presence of at least 3/68 tender and at least 3/66 swollen joints, as determined by the Tender and Swollen Joint Count Assessment Form (Section 10.7) at Visit 1 (Screening) and Visit 2 (Week 0, baseline).
- [11] Presence of active PsO or a documented history of psoriasis.

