8.1.1.2. Static Physician Global Assessment

The sPGA is the physician's determination of the participant's psoriatic lesions, overall, at a given time point. The sPGA is recommended as an endpoint to assess efficacy in the treatment of PsO/PsA (EMA 2004). Overall, lesions are categorized by descriptions for induration, erythema, and scaling. For the analysis of responses, the participant's PsO/PsA is assessed as clear (0), minimal (1), mild (2), moderate (3), severe (4), or very severe (5).

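### The Week 12 sPGA (0,1) summary for PsA participants with BSA of 3% or more sets no baseline sPGA condition, so a participant who enters at sPGA 1 and stays there can count as a responder

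*Protocol*

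**What the plan says.** **Endpoint.** Section 3 lists, under the psoriasis group, "Proportion of participants with an sPGA score of 0 or 1 (0, 1) at Week 12". This is a score at a time point, with no required change from baseline. Section 9.5.3 describes it as a response that participants achieve: "The proportion of participants achieving sPGA response of 0 or 1 at Week 12".

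**Analysis sets.** Section 9.5.3 summarizes the endpoint for PsO with no active PsA (mITT) and also "for the active PsA indication and will be based on the active PsA – mITT population with BSA of PsO" of at least 3% at baseline. Section 9.2 gives the active PsA mITT population as "defined as all enrolled participants with an Active PsA indication who receive at least 1 dose of study treatment"; no skin score enters that definition.

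**Entry criteria (Section 5.1).** Criterion [7], under the PsO heading, begins "Have both an sPGA score of" 3 or more and adds PASI of at least 12, at screening and at baseline. The only skin criterion for PsA participants is [11]: "Presence of active PsO or a documented history of psoriasis". Section 4.1 gives a separate regimen to "PsA participants who do not meet criteria of moderate-to-severe PsO", so their enrolment is by design.

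**Scale.** In Section 8.1.1.2 the sPGA runs from 0 (clear) through 1 (minimal) and 2 (mild) to 5 (very severe), and it grades induration, erythema and scaling. Section 8.1.1.3 defines BSA as the percentage of the body surface involved.

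**Missing data.** Under Section 9.3.1 a participant is a nonresponder if the criterion is not met, the data are missing, treatment stopped before the time point, or there is no postbaseline observation. Participants already at target at baseline are not mentioned.

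**The concern.** BSA measures extent and sPGA measures lesion severity, so a BSA filter of 3% does not exclude someone whose lesions are graded minimal. The eligibility rules make such entrants plausible. PsO participants must be off systemic psoriasis therapy for 4 weeks and off most topical treatment for 2 weeks (criterion [42]). PsA participants may enter on a stable conventional DMARD such as methotrexate (criteria [46] and [49]), so their skin may already be partly controlled.

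For a PsO participant, reaching 0 or 1 from 3 or more means a fall of at least two grades. For a PsA participant who enters at 1 it needs no fall at all. The PsA subset figure then mixes participants who responded with participants who were at target from the start, under a label that suggests improvement. A reader of the study report could not separate the two. PASI 75, reported for the same subset at the same visit, is anchored to baseline and does not have this problem.

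**Working it through.** **The protocol's own figure.** Section 9.7 plans 250 participants (PsO 150, PsA 100) with about 10% discontinuing: 250 × (1 − 0.10) = 225 completers, as stated. The protocol gives no expected rate or subset size for the sPGA endpoint.

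**Who can be affected.** Participants meeting the moderate-to-severe definition (PASI ≥12, sPGA ≥3, BSA ≥10%) enter at sPGA 3 or more and cannot be. That leaves PsA participants with BSA ≥3% who do not meet it. A baseline sPGA of 0 with BSA ≥3% is implausible, so in practice the case is sPGA 1.

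**Inputs, all assumed except where noted.**
- f: share of the PsA BSA ≥3% set with baseline sPGA ≤1; 5%, 10%, 20%.
- s: fraction of these counted as responders at Week 12; 0.90. This borrows the 10% discontinuation in Section 9.7 as the share lost to nonresponder imputation. That figure refers to 24 weeks, so it is only illustrative at Week 12.
- r: response rate, after nonresponder imputation, among those with baseline sPGA ≥2; 40%, 60%, 80%.

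**Formula.** The reported rate is f·s + (1 − f)·r. The rate among participants able to respond is r. The difference is f(s − r).

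| f | r = 40% | r = 60% | r = 80% |
|---|---|---|---|
| 5% | 0.05 × 0.50 = 2.5 points | 0.05 × 0.30 = 1.5 | 0.05 × 0.10 = 0.5 |
| 10% | 0.10 × 0.50 = 5 | 0.10 × 0.30 = 3 | 0.10 × 0.10 = 1 |
| 20% | 0.20 × 0.50 = 10 | 0.20 × 0.30 = 6 | 0.20 × 0.10 = 2 |

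The range is 0.5 to 10 points. The sign follows s − r. If, say, s were 0.70 and r 0.80, then with f = 10% the difference would be 0.10 × (−0.10) = −1 point.

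**Null case.** If nobody's skin changed, the reported rate would be f × 0.90: 4.5%, 9% and 18% for f of 5%, 10% and 20%.

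**Precision cost of restricting.** Take an assumed subset of 60, f = 10% and r = 60%. Unrestricted, the rate is 0.10 × 0.90 + 0.90 × 0.60 = 0.63, and the 95% half-width is 1.96 × √(0.63 × 0.37 / 60) = 12.2 points. Restricted to 54 participants at 0.60, it is 1.96 × √(0.60 × 0.40 / 54) = 13.1 points.

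**The case against.** **The SAP could settle it.** Section 9.5.3 applies unless otherwise specified and leaves further details to the SAP, which is not at hand and might add a baseline condition. That is possible. But the protocol itself fixes the endpoint, the population and the single baseline skin filter, and it is this combination that lets a non-improver count. It is more than a detail left for later.

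**The endpoint is a status.** As a proportion at 0 or 1 at Week 12 it is estimated without bias, and PASI 75 already gives a baseline-anchored skin response in the same subset. This is correct, so the inflation should be stated relative to participants who can respond. It still matters, because 9.5.3 presents the figure as a response achieved.

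**Stronger readings that a reader might infer, and that the documents do not support:**
- *Every participant entering at sPGA 1 is a responder.* Section 9.3.1 makes them nonresponders if they worsen above 1, are not assessed, or stop treatment before Week 12.
- *The named secondary endpoint is biased.* Section 3 lists sPGA (0,1) for the psoriasis group, whose entry criterion requires sPGA of at least 3.
- *A comparison between PsO and PsA is spoiled.* None is planned: Section 9.1 has no hypothesis testing and 9.5.3 summarizes the sets separately. They also differ in BSA at entry, in disease and, for the affected participants, in induction regimen. A baseline sPGA floor would not make them comparable.
- *The shift is always upward.* It is upward only if s exceeds r.

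**The size is assumed and smaller than the sampling error.** No document figure says how many PsA participants enter at sPGA 1. In the 60-participant example the half-width of about 12 points exceeds every shift in the table. Both statements stand. A systematic shift is nevertheless not conveyed by the confidence interval, and this one can be removed.

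**Conclusion.** The point holds for one descriptive summary: sPGA (0,1) at Week 12 in active PsA participants with baseline BSA of at least 3%. As written, a participant in that set who enters at sPGA 1 and remains at 0 or 1, assessed and on treatment, is reported as a responder without improvement.

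The size is f(s − r), or 0.5 to 10 percentage points over the assumed ranges, with the direction conditional on s > r. If no PsA participant with BSA ≥3% enters at sPGA 1 or below, the effect is zero; nothing in the protocol guarantees or rules that out. The primary safety analysis, the PsO-group sPGA endpoint and PASI 75 are unaffected, and with no hypothesis test there is no type I error consequence.

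**What to change.** In Section 9.5.3, for the active PsA mITT set with baseline BSA of at least 3%:

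- report sPGA (0,1) at Week 12 among participants with baseline sPGA of at least 2;
- state how many participants are excluded because their baseline sPGA is 1 or below;
- add a supportive figure for baseline sPGA of at least 3, the level required of PsO participants at entry.

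This takes a sentence or two and no new data, since sPGA is scheduled at Week 0 for PsA participants (Section 1.3). The cost is a somewhat smaller denominator and a slightly wider interval: 12.2 to 13.1 points of half-width in the 60-participant example. It also leaves some treated participants out of an mITT-based summary, which is why the number excluded should be shown beside it.
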